5.3 Treatment of subjects

5.3.1 Metformin

Metformin is an oral anti-diabetic agent in the biguanide class. In this trial metformin is characterised as background treatment (non-investigational medicinal product [NIMP]).

Subjects will undergo 3-4 weeks of metformin titration to a maximum tolerated dose (MTD) of ≥ 1000 mg and ≤ 2000 mg. Titration and MTD will be at the discretion of the investigator. It must be aimed to reach a dose of 2000 mg metformin. The titration period can be extended from 3 to 4 weeks in total, if needed for tolerability. Once MTD is reached, the metformin dose must stay unchanged throughout the trial, unless subjects meet rescue criterion no. 1 (see section [6.5](#)) The titration of metformin is followed by 8 weeks maintenance period whereafter subjects may be randomised if they fulfil the randomisation criteria (see section [6.4](#)).

Subjects treated with metformin < 2000 mg at Visit 1, may use their current dose as the starting dose for the titration. Subjects with an established MTD of ≥ 1000 mg and ≤ 2000 mg may advance directly to Visit 5. An established MTD is where previous attempts to escalate the metformin dose were not tolerated, and that the Investigator does not consider up-titration possible in the subject because of tolerability issues. Subjects treated with 2000 mg or more of metformin for less than 56 days at Visit 1 may proceed directly to the 8 weeks maintenance period.

Subjects already treated with 2000 mg or more of metformin and with a stable dose for at least 56 days prior to Visit 1 may advance directly to randomisation (Visit 7) continuing their current metformin dose when eligibility according to the inclusion and exclusion criteria has been confirmed. Subjects who are treated with basal insulin should in addition to the stable dose of metformin have a stable dose of basal insulin for at least 56 days to advance directly to Visit 7.

Metformin should be temporarily discontinued in subjects undergoing radiologic studies involving intravascular iodinated contrast materials (see local label).

5.3.2 Liraglutide

Liraglutide and liraglutide placebo are administered once daily by s.c. injections, either in the abdomen, thigh or upper arm. The injection site does not have to be consistent throughout the trial. Injections can be done at any time of the day and irrespective of meals. It is recommended that the time of injection is consistent throughout the trial. Subjects will be instructed to perform an air shot before the first use of a new prefilled pen. Liraglutide vehicle will be used as placebo. In this trial liraglutide and liraglutide placebo are characterised as investigational medicinal products (IMPs).

After randomisation, liraglutide or liraglutide placebo will be escalated weekly starting at 0.6 mg and increasing with 0.6 mg increments over 2-3 weeks. Dose escalation will be based on tolerability (dose should not be increased in case severe intolerability is experienced, as judged by the investigator) and the following: the average of 3 measurements of FPG > 6.1 mmol/L (110 mg/dL) performed by the subject at home on the three consecutive days preceding the dose escalation visit (Visits 8, 9 and 10, please see [Figure 5-2](#)). After end of the liraglutide dose escalation period no further dose escalations must be performed.

Subjects treated with basal insulin experiencing hypoglycaemia should reduce the dose of basal insulin (if needed to 0 units) before the dose of liraglutide/liraglutide placebo is decreased.

[figure not shown]

Figure 5–2 Dose escalation of liraglutide

During the blinded period, escalation at each YES/NO decision point should be determined by whether the subjects average FPG is > 6.1 mmol/L (110 mg/dL).

In the event that a subject experiences severe intolerance or recurrent hypoglycaemia as judged by the investigator (such as ≥ 3 unexplained minor hypoglycaemic events or 1 severe unexplained hypoglycaemic event in a week) the dose will be lowered to the next decreased level (from 1.8 mg to 1.2 mg or from 1.2 mg to 0.6 mg). The reason for down escalation of liraglutide must be documented in the subject's medical record and transferred to the eCRF.

If a subject treated with 0.6 mg experiences severe intolerance or recurrent hypoglycaemia as judged by the investigator (such as ≥ 3 unexplained minor hypoglycaemic events or 1 unexplained severe hypoglycaemic event in a week) the subject must be withdrawn from the trial.

5.3.3 Basal insulin

Subjects may enter the trial on a stable dose of basal insulin. A stable dose of basal insulin (intermediate acting human insulin, intermediate acting insulin analogue or long acting insulin analogue) is defined as basal insulin adjustments up to 15% at the investigator's discretion. Subjects treated with basal insulin must initiate treatment with metformin as described in section 5.3.).

The pre-trial basal insulin regimen will be considered background medication and will not be provided by Novo Nordisk.

Subjects treated with basal insulin at screening should reduce their basal insulin dose by 20% at randomisation.

Subjects on a stable dose of metformin ≥ 2000 mg as per section 5.3.1 can advance directly to maintenance period or randomisation depending on the time on stable insulin:

- Subjects with a stable dose of basal insulin for at least 30 days but less than 56 days at screening (visit 1) may proceed directly to the 8 week maintenance period (Visit 5)
- Subjects on a stable dose of basal insulin for 56 days or more at screening (Visit 1) may advance directly to randomisation (Visit 7) when eligibility according to the inclusion and exclusion criteria has been confirmed.

After the MTD dose of liraglutide/liraglutide placebo is reached, the dose of basal insulin can be up-titrated to no higher than the screening dose level. This up-titration will be based on the average of three pre-visit fasting SMPG values before visits between weeks 4 and 8 (Visits 10A -11B). Up-titration is only allowed between Visits 10A and 11B. Up-titration of basal insulin dose is to be performed at the discretion of the investigator in accordance with the algorithm described in Table 5-1.

Table 5–1 Algorithm for up-titration of basal insulin dose

Average fasting SMPG	Increase in basal insulin dose
>10 mmol/L (>180 mg/dL)	+6 units
7.8 to 10 mmol/L (141–180 mg/dL)	+4 units
6.7 to <7.8 mmol/L (121–140 mg/dL)	+2 units
5.6 to <6.7 mmol/L (100–120 mg/dL)	+1 units

SMPG=self-measured plasma glucose

(adapted from the Texas Diabetes Council 2013²¹)

Basal insulin should be down-titrated for unexplained hypoglycaemia ≤ 3.9 mmol/L (≤ 70 mg/dL) at any time during the trial at the discretion of the investigator in accordance with Table 5-2

Table 5–2 Algorithm for down-titration of basal insulin dose

PG	Reduction of basal insulin dose
One or more values < 3.1 mmol/L (56 mg/dL) without obvious explanation	Reduce insulin dose by 4 units (if dose >50 units, a dose reduction of 10% is suggested)
One or more values between 3.1–3.9 mmol/L (56–70) mg/dL) without obvious explanation	Reduce insulin dose by 2 units (if dose > 50 units, a dose reduction of 5% is suggested).

PG=plasma glucose

The basal insulin dose can be increased again to the dose the subject was on prior to the hypoglycaemic event if safety allows and at the discretion of the investigator. Subjects should continue in the trial even if the insulin treatment is down-titrated to 0 U. Subjects will be instructed to contact the investigator in case of hypoglycaemia.

No shifts in type of insulin will be allowed during the trial and for the 30 days prior to screening.

5.3.4 Open Label period

After 26 weeks of treatment, treatment allocation will be unblinded. The open-label period will last for 26 weeks until the end of treatment (week 52).

Subjects treated with liraglutide will continue their trial medication under the same circumstances as listed above for the blinded period.

Subjects treated with liraglutide placebo will discontinue liraglutide placebo and continue their treatment with MTD of metformin with or without basal insulin.

The total duration of treatment with liraglutide will be 52 weeks for subjects randomised to liraglutide. The total duration of treatment with liraglutide placebo will be 26 weeks for subjects randomised to liraglutide placebo.

5.3.5 Rescue treatment

Subjects experiencing confirmed hyperglycaemia as per rescue criterion no. 1 (see section [6.5](#)), will be offered rescue treatment. Subjects on rescue treatment will remain in the trial.

Rescue treatment will be as follows:

- Subjects treated with metformin and liraglutide/liraglutide placebo may have basal insulin added. The start dose and basal insulin titration will be at the discretion of the investigator. If subjects continue to experience confirmed hyperglycaemia as

per rescue criterion no. 1 a rapid acting insulin may be added and titrated at the discretion of the investigator.

- Subjects treated with metformin, basal insulin and liraglutide/liraglutide placebo may have the basal insulin dose increased; the dose and basal insulin titration will be at the discretion of the investigator. If subjects continue to experience confirmed hyperglycaemia as per rescue criterion no 1 a rapid acting insulin may be added and titrated at the discretion of the investigator.

If hyperglycaemia is persistent and meets the withdrawal criterion no. 5 despite rescue treatment having been initiated, the subject must be withdrawn from the trial (see section [6.5](#))

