6.5 Rescue criteria

If the fasting SMPG values taken on 3 consecutive days or any of the FPG samples analysed by the central laboratory exceeds the limits of >12.2 mmol/L (220 mg/dL) during the first 14 weeks after randomisation (after end of liraglutide dose escalation, i.e. the subject has reached 1.8 mg or the MTD, and after week 8 for subjects on basal insulin) or >10.3 mmol/L (185 mg/dL) after week 14

the subject should be called for an unscheduled visit as soon as possible. A confirmatory FPG should be obtained and analysed by the central laboratory. The unscheduled visit should be documented in the eCRF. If the FPG exceeds the above described values and no intercurrent cause for the hyperglycaemia has been diagnosed rescue treatment should be initiated according to section [5.3.5](#). If hyperglycaemia is persistent and meets the FPG limits as set above after rescue treatment having been initiated, the subject must be withdrawn from the trial (see section [6.6](#))

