6.6 Withdrawal criteria

A subject must be withdrawn if the following applies:

1. The subject may withdraw at will or be withdrawn by the subject's LAR at any time
2. The subject may be withdrawn from the trial at the discretion of the investigator due to a safety concern or if judged non-compliant with trial procedures
3. The subject must be withdrawn if randomised in error
4. Pregnancy or intention to become pregnant
5. If the subject experiences persistent hyperglycaemia despite initiation of rescue treatment as described in section [6.5](#) the subject must be withdrawn. Persistent hyperglycaemia: If fasting SMPG values taken on 3 consecutive days or any FPG samples analysed by the central laboratory exceeding the limits set below the subject must be called for an unscheduled visit as soon as possible. A confirmatory FPG must be obtained and analysed by the central laboratory. If the confirmed FPG exceeds the below described values and no intercurrent cause for the hyperglycaemia has been diagnosed the subject is experiencing persistent hyperglycaemia. The unscheduled visit must be documented in the eCRF.

FPG limits:

- during the first 14 weeks after randomisation (after end of liraglutide dose escalation, i.e. the subject has reached 1.8 mg or the MTD): FPG > 12.2 mmol/L (220 mg/dL)
 - after week 14: FPG >10.3 mmol/L (185 mg/dL)
6. Subjects who need to have their dose of metformin reduced due to tolerability after having reached their MTD must be withdrawn.
 7. Subjects treated with 0.6 mg of liraglutide who experience severe intolerance or recurrent hypoglycaemia as judged by the investigator (such as ≥ 3 unexplained minor hypoglycaemic events or 1 unexplained severe hypoglycaemic event in a week) must be withdrawn

8. Calcitonin ≥ 50 ng/L. A referral to a specialist in thyroid disease is recommended (See Appendix D)
9. If the investigator suspects acute pancreatitis, all drugs suspected to relate to this condition should be discontinued until confirmatory tests have been conducted and appropriate treatment should be initiated. Subjects that are diagnosed with acute pancreatitis and/or exhibit at least 2 of the following criteria must be withdrawn from the trial; 1) abdominal pain, 2) amylase and/or lipase $> 3x$ UNR or 3) characteristic findings on ultrasound, computerised axial tomography (CT) or magnetic resonance imaging (MRI)

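### Once rescue has started, Protocol Sections 5.3.5 and 6.5/6.6 attach two consequences to the same confirmed hyperglycaemia (add rapid-acting insulin and stay, or be withdrawn), and nothing separates them

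*Protocol*

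**What the plan says.** **The rule to stay.** Protocol Section 5.3.5 states "Subjects on rescue treatment will remain in the trial". It then describes rescue in two insulin steps. Basal insulin is added, or increased if the subject already uses it. For a subject who is still hyperglycaemic it continues: "If subjects continue to experience confirmed hyperglycaemia as per rescue criterion no. 1 a rapid acting insulin may be added". Section 5.1 likewise keeps rescued subjects on the trial schedule, and Section 5.2 gives better retention as a reason for having a rescue criterion.

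**The rule to leave.** The last sentence of Section 5.3.5 reads "If hyperglycaemia is persistent and meets the withdrawal criterion no. 5 despite rescue treatment having been initiated, the subject must be withdrawn from the trial". Section 6.5 says "If hyperglycaemia is persistent and meets the FPG limits as set above after rescue treatment having been initiated, the subject must be withdrawn". Section 6.6, criterion 5, opens with "If the subject experiences persistent hyperglycaemia despite initiation of rescue treatment as described in section" 6.5 and makes withdrawal mandatory.

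**The limits.** In Section 6.5 the trigger is a fasting value that "exceeds the limits of >12.2 mmol/L (220 mg/dL) during the first 14 weeks after randomisation" "or >10.3 mmol/L (185 mg/dL) after week 14". The first limit starts only after dose escalation, and after week 8 for subjects on basal insulin. Criterion 5 in Section 6.6 lists the same two limits.

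**The data rules.** Protocol Section 17.3 and SAP Section 3.5 use every available HbA1c in the primary analysis, including values after rescue. Under Protocol Section 8.1.7 a subject withdrawn before Visit 17 has the Visit 17 procedures straight away. Under Protocol Section 17 and SAP Section 3.2 such a measurement counts only within 5 days of a planned visit. A missing week-26 value is imputed from regression models fitted on placebo completers.

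**The concern.** A subject starts rescue and later has another confirmed FPG above the limit. One part of the protocol offers a further insulin step with the subject staying in; another part says the subject must leave. An investigator cannot follow both, and nothing tells two investigators to choose alike.

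Two things are at stake. The first is consistent care of children under one protocol. The second is the primary endpoint. SAP Section 4.1 names a treatment-policy estimand, which relies on observing outcomes after rescue. If the event falls before the Visit 17 window, the rule a site applies can settle whether the week-26 HbA1c is observed or modelled. Rescue was introduced partly to retain subjects, and the withdrawal text works against that purpose.

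**Working it through.** **Step 1. Compare the triggers after rescue has started.**

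| Element | Second insulin step (5.3.5, through the rescue criterion in 6.5) | Withdrawal (6.5 last sentence; 6.6 no. 5) |
|---|---|---|
| Screen | Fasting SMPG on 3 consecutive days, or a central FPG | Same |
| Confirmation | Central-laboratory FPG at an unscheduled visit | Same |
| Limit, first 14 weeks | Above 12.2 mmol/L | Same |
| Limit, after week 14 | Above 10.3 mmol/L | Same |
| Intercurrent cause | Must be absent | Same |
| Prior rescue | Started, still hyperglycaemic | Started |
| Minimum time on rescue | None given | None given |
| Second insulin step already tried | Not applicable | Not required |
| Consequence | May add rapid-acting insulin; stays | Must be withdrawn |

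The only wording difference is the week-8 clause for basal-insulin users, which stands in 6.5 and not in 6.6. Criterion 5 presupposes rescue, so that clause does not separate the rules once rescue has begun.

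**Step 2. Ask whether the word persistent separates them.** Section 6.6 defines it as a confirmed FPG above the limit without an intercurrent cause. It gives no duration and no number of failed steps. Every subject who qualifies for the second insulin step therefore also qualifies for mandatory withdrawal. Read literally, the second step has no case left to apply to.

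The drop in the limit at week 14 makes the overlap easier to reach. A rescued subject at, say, 11 mmol/L is below 12.2 and above 10.3, and so crosses from acceptable to exceeding without any worsening.

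**Step 3. Check the cross-references.** Section 5.3.5 sends the reader to 6.5 for withdrawal criterion 5, which stands in 6.6. Several sections cite a rescue criterion numbered 1, but 6.5 contains no numbered criteria. The references do not resolve the conflict.

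**Step 4. Follow the data for an event before the Visit 17 window.**

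- Subject stays: the week-26 HbA1c, if measured, enters the primary analysis as observed, with rescue included.
- Subject is withdrawn: the end-of-blinded-treatment measurements are taken at once. Unless that falls within 5 days of week 26, the week-26 value is missing.
- Imputation then depends on the arm. Liraglutide subjects get the baseline-only model (model 1). Placebo subjects get model 2, 3 or 4 where they have their own week-10 or week-14 HbA1c. All models are fitted on placebo completers.

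Events after the Visit 17 window can affect week 52 only.

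**Step 5. Is there a figure to attach?** The plan's own figure reproduces. Inputs from Protocol Section 17.1: difference 0.9, SD 1.2, active-arm withdrawal 22%, two-sided 5%, 47 per arm. Adjusted difference = 0.9 × (1 − 0.22) = 0.702. The two-sample t-test, with noncentrality 0.702 / (1.2 × √(2/47)), has power 80.1% and needs 47 per arm, 94 in total. The same method returns all 15 sample sizes in Table 17-1.

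No document says how many subjects would meet both rules. To show how sensitive a trial of this size is, assume that k liraglutide subjects more or fewer are withdrawn. Use the planning convention that a withdrawn liraglutide subject contributes zero effect and a retained one contributes 0.9. Each subject then moves the adjusted difference by 0.9 / 47 = 0.019.

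| k | Adjusted difference, k more | Power | Adjusted difference, k fewer | Power |
|---|---|---|---|---|
| 1 | 0.683 | 77.9% | 0.721 | 82.2% |
| 3 | 0.645 | 73.1% | 0.759 | 85.9% |
| 5 | 0.606 | 67.9% | 0.798 | 89.0% |

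This is a scale, not an estimate. A subject who exceeds the limit on rescue may well not carry the full 0.9, in which case withdrawal costs less. If the retained subject would have done worse than placebo, withdrawal would raise the difference.

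**The case against.** **A staged reading is available.** Section 5.3.5 lists basal insulin, then rapid-acting insulin, and only then withdrawal, and that order suggests escalation. It may be what was intended. But no sentence makes withdrawal wait for the second step: 6.5 and 6.6 tie it to rescue having been initiated, which is already true after the first step. Nor does it help that one text permits and the other obliges. If the obligation always prevails, the permission is empty. What stands of this objection is that differing practice is a possibility and not a certainty.

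**The sensitivity analyses limit the exposure.** In SAP Section 3.5, analyses 1, 3, 4 and 5 discard data after rescue, so staying or leaving after rescue adds no data to four of the six. This is correct, and it is useful as a check. Those analyses set aside the post-rescue data that the treatment-policy estimand calls for, so they do not settle the primary analysis, nor analyses 2 and 6, which keep those data.

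**The stronger reading.** A reader might infer that the conflict biases the trial towards liraglutide, because poorly controlled placebo subjects would be withdrawn and replaced by better-controlled completers. The documents do not support this, for five reasons:

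- The remark in Protocol Section 3.1.5 about an expected need for rescue on placebo explains the unblinding after week 26. It does not forecast the split between arms before week 26.
- Withdrawn placebo subjects are imputed from their own week-10 and week-14 values where these exist, so part of their poor control would carry over.
- Retained subjects would have insulin titrated by the investigator. Their week-26 HbA1c could be above, equal to or below that of completers.
- Rescued placebo subjects who stay may be among the completers on whom the models are fitted.
- Replacing poorly controlled liraglutide subjects by placebo-based values could move the contrast in either direction.

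**Conclusion.** The contradiction is in the text and does not depend on any assumption. For the same confirmed exceedance after rescue has started, the protocol both keeps the subject in and requires withdrawal, and sites that follow it may act differently. The consequence for the primary endpoint is confined to events before the Visit 17 window. There the rule applied can determine whether week-26 HbA1c is observed or imputed.

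The size and direction of any effect on the treatment difference cannot be derived from the documents. The power figures above rest on an assumed number of subjects and on the planning convention for withdrawn liraglutide subjects. They show only that a handful of subjects matters with 47 per arm. The sample size calculation itself is correct. The point deserves correction because it puts two incompatible instructions before investigators treating children and costs little to resolve.

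**What to change.** Reconcile Protocol Sections 5.3.5, 6.5 and 6.6 (criterion 5) so that exactly one consequence follows a confirmed exceedance after rescue has started. If both the second insulin step and withdrawal are to remain, state what separates them. Which clinical rule applies is for the sponsor to decide.

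In the same change, correct the cross-references: point withdrawal criterion 5 to Section 6.6, and either number the rescue criterion in 6.5 or stop citing it by number.

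The cost is a wording amendment or a clarification to sites. It needs no additional subjects, visits or samples, and no change to the sample size.

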5.4 Rationale for treatment

Liraglutide escalation and doses used in the present trial have been chosen based on results from the NN2211-1800 trial performed in children and adolescents as described below, and on the current approved labelling for Victoza^{®15}.

In the NN2211-1800 trial liraglutide treatment or corresponding volume of placebo was initiated with 0.3 mg/day for the first week. The dose was escalated weekly to 0.6, 0.9, 1.2 and 1.8 mg/day of liraglutide or placebo. Dose escalation took place only if the mean fasting plasma glucose (FPG) taken on three consecutive days before the dose escalation visits was above 6.1 mmol/L (110 mg/dL). Nine (9) liraglutide subjects escalated to the maximum dose of 1.8 mg liraglutide, while 3 subjects remained on 0.6 mg liraglutide. One (1) subject, who was diet and exercise treated, remained on 0.3 mg liraglutide (HbA_{1c} of █% at screening). The decision to escalate subjects to the maximum dose of 1.8 mg was based on FPG measurements, and not on lack of tolerability or AEs. All subjects randomised to placebo were escalated to a dose volume corresponding to 1.8 mg liraglutide. Two subjects (one treated with liraglutide and one with placebo) withdrew prematurely from treatment for other reasons than tolerability (blood draw issue and did not want to undergo procedures).

The American Diabetes Association (ADA) recommends the use of metformin in 2000 based on the efficacy and safety data for adults²⁴ Metformin is the ADA preferred first oral agent because it does not induce hypoglycaemic events. In 2002 a trial demonstrated the safety and efficacy of metformin in children and adolescent and concluded that the efficacy and safety profile was similar to the adult population². Metformin doses of ≥ 1000 mg and ≤ 2000 mg have been shown to have an acceptable safety and efficacy profile in children and adolescent and these doses were therefore chosen for this trial. The use of 2500 mg of metformin has only been tested in adults where FPG was slightly reduced. Therefore doses higher than 2000 mg of metformin will only be permitted for subjects entering the trial with a dose > 2000 mg at the time, if in accordance with local standard of care.

Insulin therapy is a key component in the treatment of children and adolescents with type 2 diabetes²⁵. The SEARCH incidence study identified 119 adolescents between 10-19 years of age, 31.1% of whom (GAD65 negative) were being treated with insulin²⁶. Recent guidelines recommend that insulin therapy be initiated in children and adolescents who have random venous or plasma blood glucose levels > 250 mg /dL, or whose HbA_{1c} >9%, and certainly in patients who exhibit ketosis or ketoacidosis²⁷. An earlier recommendation was to treat patients with blood glucose >200 mg/dL, HbA_{1c} more than 8.5%, or severe manifestations of insulin deficiency (e.g. ketosis/diabetic ketoacidosis) with insulin initially to achieve metabolic control rapidly. After resolution of ketosis (hydration and treatment with insulin, metformin should be started and insulin may be gradually weaned if normoglycaemia is maintained²⁸.

Inclusion of children and adolescents with type 2 diabetes with basal insulin in this clinical trial is consistent with clinical practice^{25, 27}.

6 Trial population

